1. INTRODUCTION

1.1. Background and Significance

Pancreatic cancer is the twelfth most common cancer worldwide, with about 45,220 new cases diagnosed in the US in 2013 [1,2]. Given its nonspecific subtle presentation, close to 50% of patients with pancreatic cancer unfortunately have metastatic disease by the time of their presentation, with average 5-year survival of approximately 6% [2].

Neoadjuvant chemoradiation therapy in patients with borderline resectable pancreatic adenocarcinoma has become standard of care and is associated with higher rates of complete resection without microscopic evidence of residual tumor (R0 resection), lower rates of lymph node positivity, and improvement of overall survival in this patient population [3,4]. Radiation therapy to a soft tissue organ such as the pancreas can be difficult, as it is not readily visualized radiographically. In the past, bony structures have been used as surrogate markers for approximation of the pancreas. However, respiratory variation can lead to large differences in tumor location leading to suboptimal radiation delivery and radiation of healthy tissue. Thus, image guided radiation therapy (IGRT) is a commonly implemented modality for delivering high doses of radiation directed at cancer tissue, while reducing collateral damage to adjacent healthy tissue [5,6]. Fiducials, which are inert radiographic markers typically made from gold or carbon, can be placed in and around the tumor to delineate tumor margins to allow for IGRT.

Endoscopic ultrasound (EUS) has been pivotal in accomplishing IGRT by allowing precise contouring and identification of target lesions in the pancreas via placement of fiducials. This has traditionally been accomplished with the use of 19-guage or 22-guage fine needle aspiration (FNA) needles [7-14]. To prepare the needle for fiducial placement, one to two fiducials are manually back-loaded into the tip of the needle after the stylet has been removed. Different size fiducials are used for different gauge needles. In order to hold the fiducials within the needle, sterile lubrication or bone wax can be applied [21]. Once the pancreatic mass has been targeted, fiducial injection can be accomplished via stylet reinsertion or sterile water injection [15,16].

Currently, back-loading the fiducials is the only option for preparing delivery of fiducials via the EUS approach. Difficulties associated with fiducial loading and deployment can increase procedure duration due to cumbersome fiducial back-loading, fiducial misplacement & migration, as well as inability to pass the fidicual marker through the needle due to endoscope angulation.

Multiple observational studies ranging from 7 to 57 patients have sited a technical success rate of 86-100% using 19 and/or 22 gauge needles [8,10-14, 17-19], with average procedure time between 7-12 minutes [12] using the fiducial back-loading technique.

A new mode of fiducial delivery has recently been developed that hopes to circumvent some of the technical issues inherent to traditional fiducial marker loading and deployment. In a feasibility study by Draganov et al, a prototype 22-Gauge EUS needle preloaded with four fiducials were used in a porcine model to test ease of deployment, technical success, accuracy, EUS visualization of the needle, fiducial visualization on EUS as well as fluoroscopy and CT, as well as time for placement and adverse events. Fiducial deployment was successful 95.6% of the time with all 172 fiducial markers deployed on predetermined targets. Using a 5 point Likert scale, needles were deemed easy to pass, relatively easy to COMIRB Protocol #14-1711 PI: [name] MD Version Date: 01/23/2019

deploy, and easily visualized on EUS, with excellent fluoroscopic and CT visualization. In addition, time for deployment was on average less than 60 seconds.

To date, there is no randomized controlled trials comparing total duration of time needed for placement of fiducials using the traditional back-loading technique of fiducial markers to the new preloaded needles in regards to EUS based fiducial marker placement for IGRT in pancreatic cancer.

1.2 Hypotheses and Endpoints

Hypotheses

- 1) Use of a 22 G preloaded needle for EUS guided fiducial marker placement in patients with pancreatic cancer will be delivered in at least 60% of the procedure time that it takes for traditional back-loaded 22G needles, improving overall procedure efficiency.
- 2) Use of a 22 G preloaded needle for EUS guided fiducial marker placement in patients with pancreatic cancer will maintain comparable technical success and adverse event rates when compared to traditional back-loaded 22G needles.

Primary Aims

1) To compare the procedure time of 22G needle placement of three Visicoil fiducial markers and 22G needle preloaded fiducial markers.

Secondary Aims

1) To compare endpoints of technical success defined as proper placement of three fiducial markers in a pancreatic neoplasm in 22G needle placement of Visicoil fiducial markers and 22G needle preloaded fiducial markers.

2) To compare adverse event rates in 22G needle placement of Visicoil fiducial markers and 22G needle preloaded fiducial markers

1.3. Preliminary Studies/Progress Report: To date, there are no preliminary studies of the above proposed study.

2. RESEARCH DESIGN AND METHODOLOGY

A. Description of Population to be Enrolled. (Appendix AP1)

Inclusion Criteria:

• Patients with pathologically confirmed pancreatic cancer referred for IGRT.

Exclusion Criteria:

- Age <18
- Inability to consent
- Known coagulopathy/thrombocytopenia (INR >1.5, platelets <75)
- Patients on antiplatelet/anticoagulant medication that cannot safely be discontinued 5-7 days prior to the procedure
- Gold allergy
- Current infection
- EUS evidence of vessel interfering with path of fiducial marker
- Pregnancy

B. Study Design and Research Methods: Patients with pancreatic cancer referred for fiducial marker placement for IGRT will be eligible for enrollment in the study. Eligibility of study enrollment will be determined prior to the endoscopic evaluation. Subjects will be contacted via telephone before their scheduled visit to inform the subject about the study with a copy of the consent form sent to the subject prior to the EUS procedure (please see Appendix AP2 for copy of phone script). The consent form will then be reviewed in person either in the pre-operative endoscopy unit or in the gastrointestinal clinic if pre-procedure consultation was obtained. Prior to the patients undergoing EUS evaluation, patients will be excluded from the study if they meet any of the exclusion criteria as listed above. All patients who are not excluded from the study as outlined above will be eligible for the study.

Patients without a previous diagnosis of pancreatic cancer but are referred for EUS guided FNA of a suspicious for pancreatic malignancy may also be eligible if a diagnosis of pancreatic cancer can be made by an on-site by a cytopathologist, and the stage dictates that they will need IGRT based on clear discussion with the radiation oncologist, oncologist and surgeon. In this situation fiducial markers may be placed in the same setting.

DESCRIPTION OF THE PROCEDURE (Fig. 1)

Once the patient is consented for the study, randomization will then be performed using stratified (based on location of the tumor – head/neck vs. body/tail) block randomization. The patients will undergo Linear EUS, as previously described by Devila Fejardo et al. and have fiducial marker placement via a traditional 22G back-loaded needle (Visicoil) [22] or the new 22G preloaded needle (PreLoad4). Multiple endpoints will be recorded, including total length of procedure, how many markers are successfully deployed, and technical success (Ease of passage of delivery system, ease of deployment of fiducials, EUS visualization of delivery system needle, EUS visual appearance of fiducials, and time for fiducial placement defined as starting time of removing the needle from its packaging and ending time as removal of needle after final marker deployment). Procedure time will be recorded by a research assistant at each site. Fiducial marker location will be confirmed via fluoroscopy at time of placement and on 4D treatment planning CT ordered by the radiation oncologist for simulation.

Patients will be discharged home after post procedure recovery. Patients will be contacted at home by a research coordinator or endoscopy staff 24-48 hours and 7-10 days after the procedure to document any

immediate and delayed complications. Patients will return for their IGRT visit, and any evidence of fiducial marker migration will be recorded by the radiation oncologist.

For patients who have preceding diagnostic FNA, this will be recorded, with number of passes/aspiration attempts recorded as well.

Endpoints

Primary endpoints utilized in this study will be:

• To compare procedure time of 22G needle placement of three Visicoil fiducial markers and 22G needle preloaded fiducial markers.

Secondary endpoints will include:

- Technical success of fiducial marker placement in 22G back-loaded needles and 22G preloaded needles defined by proper placement of three fiducial markers in a pancreatic neoplasm.
- Rate of fiducial migration
- Ease of passage of delivery system
- Ease of fiducial deployment
- EUS visual appearance of fiducials
- Visualization as assessed by radiation oncology
- Inadvertent deployment of fiducials
- Adverse event rates recorded throughout the study period
- Descriptive comparison of outcomes across sites

Figure 1- Proposed Study Methods

C. Description, Risks, and Justification of Procedures and Data Collection Tools.

Recording of Complications

Complications will be defined as any deviation from the clinical course after the procedure. All adverse event data will be collected during the study period and graded as:

Minor: nausea, vomiting, abdominal pain

Major: perforation, pancreatitis, major bleeding, infection, transfusion secondary to major bleeding, aspiration, arrhythmia, hypotension, death

The investigator at each site will assess each adverse event with respect to severity and relationship to the study interventions. Patients will be contacted at 24-48 hours post-procedure by an experienced GI nurse to assess for complications post procedure (See Appendix AP5/6). All adverse events (whether or not considered device-related) must be reported immediately (within 48 hours) to the study coordinator, confirmed in writing by the Investigator and recorded in the Adverse Events section of the case report form (CRF). Those adverse events that meet the criteria for a Serious Adverse Event will be reported additionally on a Serious Adverse Event CRF. The investigator at each site will make the determination regarding reportability of any AE or SAE to their respective IRB. The University of Colorado will be the central site for all SAE reporting at any site within 24 hours of the occurrence. They will also control randomization, and receive/manage AE/SAE reporting and DSMC. A group of PIs at the cancer center DSMC will review all reports every 6 months. SAE reporting will be reviewed within 24 hours, and all sites and IRBs (per IRB policy) will be informed within a 12-24 hour period of the event and review regarding whether the SAE was thought to be potentially related to the study/new device.

Monitoring and Oversight

The sponsor investigator will be responsible for monitoring the trial per the trial monitoring plan, in addition to overseeing the safety and efficacy of the trial including any specimens collected, executing the data and safety monitoring (DSM) plan, and complying with all reporting requirements to local and federal authorities. This oversight will be accomplished through additional oversight from the Data and Safety Monitoring Committee (DSMC) at the University of Colorado Cancer Center (CU Cancer Center). The DSMC is responsible for ensuring data quality and study participant safety for all clinical studies at the CU Cancer Center, which is the coordinating institution of this trial. A summary of the DSMC's activities is as follows:

- Conduct of internal audits
- Ongoing review of all unanticipated adverse device effects, serious adverse events (SAEs), unanticipated problems (UAPs) and reportable adverse events (AEs)
- Has the authority to close and/or suspend trials for safety or trial conduct issues
- May submit recommendations for corrective actions to the CU Cancer Center's Executive Committee

Per the CU Cancer Center Institutional DSM Plan, SAEs, UAPs and reportable AEs are reported to the DSMC, IRB and the sponsor investigator per protocol. All SAEs, UAPs and reportable AEs including unanticipated adverse device effects are to be reported to the DSMC within 5 business days of the sponsor investigator receiving notification of the occurrence.

Each subject's treatment outcomes will be discussed by the site PI and appropriate staff at regularly scheduled meetings. Data regarding number of subjects, adverse device effects, treatment modifications and treatment responses will be discussed and documented in the meeting's minutes. The sponsor investigator is responsible for organizing and conducting regularly scheduled teleconferences with all participating sites. The sponsor investigator will also be responsible for including data from all of the participating sites to include the minutes from these regularly scheduled teleconferences between the sponsor investigator and the sites within the overall trial's six month DSM report.

The sponsor investigator will provide a DSM report to the CU Cancer Center DSMC on a six month basis. The DSM report will include a protocol summary; current enrollment numbers; summary of adverse device effects to include specific unanticipated adverse device effects, SAEs, UAPs and AEs; any treatment modifications; all protocol deviations; and protocol amendments. The DSM report submitted to the DSMC will also include, if applicable, the results of any efficacy data analysis conducted. Results and recommendations from the review of this six month report by the DSMC will then be provided to the sponsor investigator in a DSMC review letter. The sponsor investigator is then responsible for ensuring this letter is submitted to the site's IRB of record at the time of IRB continuing review.

Quality Control and Quality Assurance

Site monitoring visits will be performed by the sponsor investigator's authorized representative on a regular basis, pursuant to the Monitoring Plan. During these visits, information recorded on the CRFs will be verified against source documents. Additional computer programs that identify selected protocol deviations, out-of-range data, and other data errors within the electronic data entry may also be used to help monitor the study. As necessary, requests for data clarification or correction will be sent to the appropriate site PI.

Independent auditors from the sponsor investigator's authorized representative will be allowed by the site's PI to audit. In addition, audits may be conducted at any time by appropriate regulatory authorities and/or the IRB.

Data Collection

- Demographic data collection (Appendix AP3)
 - o Age
 - o Sex
 - o BMI
 - \circ $\,$ Tumor location and size $\,$
- Likert Scale for technical evaluation (Appendix AP4)
- Adverse event collection (immediate/delayed complications- Appendix AP5/6)

At UCD, eligible patients who consent to the study will have their data captured in a password protected database through Redcap. Protected Health Information will be de-identified after extraction, and each subject assigned a unique random number. This database will be stored in a password-protected database, in a password-protected folder on the secure server behind the UCD firewall. The information will, at all times, only be able to be accessed by the primary investigator and co-investigators. All study personnel have completed HIPAA and CITI training in human subjects' research. In order to de-identify patients from their health information a spreadsheet will be created that assigns a number to each patient. The legend will be stored separately in a password-protected folder for patient numbers. Once the data COMIRB Protocol #14-1711 PI: [name] MD Version Date: 01/23/2019

collection is complete the spreadsheet containing the names and numbers will be destroyed. The deidentified information will be stored on a secure server behind the UCD firewall and will be password protected.

Regarding multicenter data, any institutional data will be shared via encrypted email to the primary site (UCD). At UCD, the Case Report Forms will be reviewed by UCD's investigators and study coordinators periodically throughout the conduct of the trial to review adverse events

D. Potential Scientific Problems.

Factors that could threaten our ability to obtain meaningful generalizable knowledge from this study would be lack of patient followup to reevaluate fiducial marker location. However, as patients are having this procedure performed for cancer therapy, it is unlikely that there will be a large proportion of patients who are lost to followup.

E. Data Analysis Plan. This section should include:

For Quantitative analyses:

i) Statistical Analysis: Categorical variables will be summarized with counts and percentages whereas continuous covariates will be summarized with means and standard deviations (SD). For evaluation of the demographic data a Fisher's exact test or Mann-Whitney U test will be performed as applicable.

ii) Success rates for each of the two arms will be calculated as a proportion of number of successfully deployed fiducial markers over the total number of patients in whom this was attempted within the study population. This will be reported as a percentage. Comparison of successful deployment of fiducial markers by two comparative groups will be performed by Fisher's exact test. Similarly, comparison between the two arms will be performed for technical success, procedure time, adverse event rate, rate of migration, ease of fiducial deployment, and visualization of needle and fiducials via EUS and CT by using Fisher's exact test. When data is ordinal, comparisons will be made using Mann-Whitney U test.

Sample Size:

Sample size calculated for the primary aim showed that in order to detect that the PreLoad4 device can be delivered in at least 60% of the time it takes to deliver a fiducial marker by back-loading, for an 80% power and alpha of 0.05 (two-sided) a minimum of 20 patients will be required in each arm.

Randomization:

Patients will undergo central block randomization (5 blocks of 4 per stratified arm at each center) stratified based on tumor location (head/neck vs. body/tail). This will be performed by a computerized binary number generator at the University of Colorado, who will control randomization for all sites. The arm that the patient will be randomized to will be determined by the above process and with the use of opaque sealed envelopes.

F. Summarize Knowledge to be Gained.

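### Randomisation follows consent, apparently before EUS, so a patient can fail an EUS-dependent exclusion after allocation and have no placement time for the intention-to-treat comparison

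*Protocol*

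**What the plan says.** The exclusion list in protocol section 2.A includes "EUS evidence of vessel interfering with path of fiducial marker". Section 2.B then fixes the timing twice: "Eligibility of study enrollment will be determined prior to the endoscopic evaluation", and "Prior to the patients undergoing EUS evaluation, patients will be excluded from the study if they meet any of the exclusion criteria". Consent is reviewed in the pre-operative unit or in clinic.

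Section 2.B also admits patients referred without a diagnosis. They "may also be eligible if a diagnosis of pancreatic cancer can be made by an on-site by a cytopathologist", and only if the stage is agreed to call for IGRT. Both facts are settled during or after the EUS session.

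The description of the procedure says "Once the patient is consented for the study, randomization will then be performed using stratified" blocks, and the linear EUS comes next in the text. The Randomization paragraph of section 2.E says that the arm is "determined by the above process and with the use of opaque sealed envelopes". It does not say when an envelope is opened. No masking of the operator is stated.

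Placement time has its "starting time of removing the needle from its packaging and ending time as removal of needle after final marker deployment". The SAP states that all analyses follow intention-to-treat and that a per-protocol analysis was also done. It defines neither set and gives no rule for a randomised patient without a placement time.

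**The concern.** Set side by side, the statements cannot all be followed. A finding made at EUS cannot be used before EUS, unless an earlier EUS exists, and the protocol does not require one. If allocation really precedes the EUS, the vessel check becomes a post-randomisation exclusion.

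Three consequences follow. First, whether a vessel interferes is a matter of judgement, and an operator who knows the arm could judge differently by arm. Second, a patient stopped at that check never has a needle unpacked, so the primary outcome does not exist and no later analysis can recover it. Third, the intention-to-treat label then has no definite meaning for the time comparison, because a reader cannot tell whether such patients were counted, dropped or replaced.

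**Working it through.** **Order of events in the text**

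1. Eligibility is decided and all exclusions are applied: before EUS (2.B).
2. Consent: pre-operative unit or clinic (2.B).
3. Randomisation: once consented (description of the procedure).
4. Linear EUS: described next. A vessel in the path is first visible here, unless an earlier EUS showed it.
5. On-site cytology and the IGRT decision, for patients without a diagnosis: during or after step 4.
6. Needle unpacked: the clock starts.

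A patient stopped at step 4 or 5 has been allocated at step 3 and never reaches step 6.

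**The planned sample size.** The protocol gives 20 per arm, 80% power and two-sided alpha 0.05, but no SD, so the figure can only be inverted. For a two-sample t-test it requires a standardised difference d = 0.909. The implied coefficient of variation (CV) is 0.40/0.909 = 0.44 if the target is 60% of the back-loaded time (protocol), or 0.60/0.909 = 0.66 if it is a 60% reduction (SAP).

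**Power after losses.** The noncentrality is d/√(1/n₁ + 1/n₂).

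| Patients with a time | Noncentrality | Power |
|---|---|---|
| 20 and 20 | 0.909/0.3162 = 2.87 | 80.0% |
| 20 and 18 | 0.909/0.3249 = 2.80 | 77.7% |
| 18 and 18 | 0.909/0.3333 = 2.73 | 75.5% |

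**Shift in the mean.** Assume lognormal times with log-SD s = √ln(1 + CV²), which is 0.421 or 0.601. Let r be the assumed correlation between difficulty and log time. If the most difficult 10% (2 of 20) leave one arm, its mean falls by 1 − Φ(1.2816 − r·s)/0.9.

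| CV | r = 0.3 | r = 0.5 |
|---|---|---|
| 0.44 | 2.7% | 4.7% |
| 0.66 | 3.9% | 7.0% |

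On the 7 to 12 minutes cited in the protocol background, this is 7 × 0.027 = 0.19 to 12 × 0.070 = 0.84 minutes. The planned reduction is 40% or 60%.

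**Type I error.** Simulation (200,000 runs), no true effect, the 2 most difficult of 20 removed from one arm only:

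| CV | r | t-test | Mann-Whitney |
|---|---|---|---|
| 0.44 | 0.3 | 5.1% | 5.0% |
| 0.44 | 0.5 | 6.0% | 5.8% |
| 0.66 | 0.3 | 4.9% | 5.2% |
| 0.66 | 0.5 | 5.6% | 5.8% |

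**How often.** The documents give no rate. If 5% of patients had such a vessel, the chance of at least one among 40 is 1 − 0.95⁴⁰ = 87%. At 2.5% it is 1 − 0.975⁴⁰ = 64%.

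**Room to replace.** The list has "5 blocks of 4 per stratified arm at each center". Read as per stratum, that is 5 × 4 = 20 per stratum, 40 per centre over two strata, and so 20 per arm at each centre. Two centres give 40 per arm. At an assumed 10% loss, 20/0.9 = 22.2, so 23 per arm would need to be randomised.

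**The case against.** The strongest reply is that the sequence may be stated elsewhere. The procedure section refers to Figure 1, which was not available for this review and may show the order. Some patients may have had an earlier diagnostic EUS that settles the vessel question. The cytology route is worded as an exception, so it need not contradict the general rule. These points stand as limits, but they do not remove the conflict in the text. A figure would not change the wording that applies every exclusion before EUS, nor would it define the analysis sets, and no passage makes an earlier EUS a condition of entry.

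Nor is the plan silent on timing. It does time randomisation, at consent. The problem therefore comes mainly from the stated order, and the missing opening time of the envelope only leaves it unresolved.

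Three stronger readings are tempting and are not supported.

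- **That such exclusions occurred, or differed by arm.** Nothing in the documents shows either.
- **That technical success would read 100% or 90% depending on the denominator.** Section 2.E does use attempted patients as a denominator, but for a rate whose numerator is markers. Three markers in each of 18 patients would be 54/18, which is not a percentage of patients. Technical success is listed separately, with no denominator given, so a conflict with intention-to-treat is not shown.
- **That the type I error could reach about 12% through arm-dependent exclusion.** Removing the two slowest of 20 from one arm (r = 1) does give 11.6% to 11.9% with the t-test. But removing the two slowest from both arms, which creates no difference between them, already gives between 9% and 10%. Most of the excess comes from trimming the upper tail, which makes the variance estimate too small. It is not a measure of arm bias.

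**Conclusion.** The point holds as an inconsistency in the order of eligibility, allocation and EUS, joined to an undefined intention-to-treat set. As written, a patient can be excluded after allocation and then has no primary outcome. The expected damage is small: type I error of about 5% to 6%, a shift in the mean of about 3% to 7%, and power of 77.7% with two losses in one arm or 75.5% with two in each. These figures rest on assumed loss rates, assumed correlations of 0.3 to 0.5, lognormal times, and a CV inferred from the sample size. The power loss can be made good, since 20 per arm is given as a minimum and the list appears to hold spare allocations. This is a cheap improvement and no threat to the trial's main conclusion. Confidence is medium, because Figure 1 could not be seen.

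**What to change.** Reconcile sections 2.A, 2.B and 2.E so that one order applies:

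- All criteria are applied before EUS, except the EUS vessel check and, for patients without a prior diagnosis, the on-site cytology and the IGRT decision.
- The sealed envelope is opened only after these checks are passed, immediately before the needle is unpacked. The start of the clock is unchanged.
- Patients who fail earlier are logged as screened and not randomised.

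In the SAP, define the intention-to-treat set as every patient whose envelope was opened, analysed in the assigned arm.

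Two additions should be avoided. A per-protocol set defined by successful placement of three markers would select on the outcome. Entering the time of a failed attempt as an ordinary value in the main time analysis could make an early abandonment look fast.

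The cost is protocol and SAP wording and a site instruction; the envelopes are already planned. Both needle types must be on hand, and opening the envelope adds a short delay. The SAP is written in the past tense. If enrolment is complete, the remedy is to report, by arm, the randomised patients without a placement time and the reason for each.

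### Success is stated inconsistently: the analysis plan's success rate divides markers by patients, so it is not a proportion, and the technical-success label is attached to two different things

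*Protocol*

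**What the plan says.** Hypothesis 2 in Protocol section 1.2 is that the preloaded needle "will maintain comparable technical success and adverse event rates when compared to traditional back-loaded 22G needles". Secondary Aim 1 in the same section speaks of "technical success defined as proper placement of three fiducial markers in a pancreatic neoplasm". The aims in the Protocol Summary use the same definition, and so does the secondary endpoint list in section 2.B ("defined by proper placement of three fiducial markers in a pancreatic neoplasm").

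The recording sentence in section 2.B, under the description of the procedure, names the endpoints to be captured, "including total length of procedure, how many markers are successfully deployed, and technical success". It then opens a parenthesis after the last of these: "technical success (Ease of passage of delivery system, ease of deployment of fiducials, EUS visualization of delivery system needle". The parenthesis goes on to "EUS visual appearance of fiducials, and time for fiducial placement defined as starting time of removing the needle from its packaging", with the clock stopping when the needle is withdrawn after the last marker.

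Section 2.E, item ii, gives a success rate for each arm: markers successfully deployed, divided by the patients in whom deployment was attempted, as a percentage. It continues, "Comparison of successful deployment of fiducial markers by two comparative groups will be performed by" Fisher's exact test. The next sentence compares technical success between arms, listed apart from procedure time, ease of deployment and visualization.

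The SAP names tests for categorical and continuous data. It mentions neither technical success nor a success rate.

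**The concern.** Technical success is one of the two outcomes in Hypothesis 2, so the plan should leave one way to count it. Two things stand in the way.

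First, the success rate in section 2.E has markers in the numerator and patients in the denominator. The result is an average number of markers per patient shown as a percentage. Fisher's exact test needs each unit to be either a success or a failure, and this ratio has no such unit. An analyst must replace the rule with something else, and the text does not say with what.

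Second, the parenthesis in section 2.B puts the technical-success label on items that are not the three-marker criterion. It also encloses the only start and stop rule for any time in either document. That rule most plausibly belongs to the primary endpoint, procedure time, but it sits under the name of a secondary one.

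At stake is whether a reader of the results can tell what a reported success percentage counts.

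**Working it through.** **Step 1. The uses side by side.**

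| Place | What success means | Unit |
|---|---|---|
| Protocol Summary, section 1.2, section 2.B endpoint list | three markers properly placed in the tumour | patient, yes/no |
| Section 2.B recording sentence | two ease items, two visualization items and a placement time, with no cut-off and no combining rule | none that gives a rate |
| Section 2.E, item ii, first measure | markers deployed ÷ patients attempted | mixed |
| Section 2.E, item ii, following list | technical success, not redefined, listed apart from time, ease and visualization | fits the first row |
| SAP | not mentioned | – |

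**Step 2. The section 2.E formula as written.** Inputs: 20 patients per arm (Protocol section 2.E and SAP) and three markers per patient (section 1.2).

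- All markers deployed: 3 × 20 = 60 markers, and 60/20 = 3.00, or 300%.
- Fisher's table would need failures = patients − successes = 20 − 60 = −40, which is impossible.
- One marker in every patient: 20/20 = 100%, although no patient then meets the three-marker definition.

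The formula therefore goes above 100% in ordinary use, and where it reads 100% it can describe complete failure on the defined endpoint.

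**Step 3. The natural repairs give different figures.** Assume for illustration that three markers are attempted in each of 20 patients and 57 of the 60 are deployed.

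- As written: 57/20 = 285%.
- Markers over markers attempted: 57/60 = 95%.
- Patients with all three, if the three losses fall in one patient: 19/20 = 95%.
- Patients with all three, if the losses fall in three patients: 17/20 = 85%.

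As a second illustration, take the 95.6% deployment rate that section 1.1 cites from the porcine study and assume that markers succeed independently. The formula as written gives 3 × 0.956 = 2.868, or 286.8%. The chance that a patient receives all three is 0.956³ = 0.874, or 87.4%. The same performance reads as 95.6% or 87.4%, depending on the repair.

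**Step 4. Marker-level testing.** Entering 60 markers per arm in Fisher's test would make the table arithmetically possible. It would also treat three markers placed in one patient with one needle type as independent, which the design does not support. The marker-level figure is suitable for description only.

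**Step 5. Where the parenthesis items appear elsewhere.** Ease of passage, ease of deployment and EUS appearance of the markers are separate secondary endpoints in the section 2.B list. EUS visualization of the needle is a secondary endpoint in the Protocol Summary and is compared in section 2.E, but it is missing from the section 2.B list. Placement time is not listed by that name; the nearest entry is the primary endpoint, procedure time.

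**The case against.** The strongest defence is that the protocol really has one definition. Each place that says technical success is defined gives the three-marker criterion. The parenthesis belongs to a sentence about recording, and without a threshold or combining rule it cannot produce a success rate. Section 2.E lists technical success beside procedure time, ease and visualization, so it does not treat those as its components. All of this stands, and the per-patient definition is very probably the intended one.

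A reader might go further and infer that technical success contains the primary endpoint, so that Hypothesis 1 (faster) and Hypothesis 2 (comparable success) collide, or that operator preference could be reported as success. The documents do not support this. No section builds a composite. Section 1.2 defines technical success next to the hypotheses. A research assistant records procedure time, so it is not an operator rating. That the other four items are scored on a Likert scale is itself an inference from the data collection list, because the appendix is not in the available text. Equating the placement time with the primary endpoint is also an inference, though a strong one, since the same sentence separately records total procedure length.

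It may also be said that nobody would report 300%, so the section 2.E formula would be put right at analysis. That is likely, but the correction could go to markers over markers or to patients over patients, and Step 3 shows that these can differ. The objection does not remove the need to state which.

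**Conclusion.** The point holds as an inconsistency in a secondary endpoint. The success rate in section 2.E is wrong as written: it reaches 300% at full success and cannot enter the test prescribed for it. In the illustration, the two natural repairs differ by up to 10 percentage points (95% against 85%). That size rests on the assumed 57 of 60 markers and on how the losses cluster; the documents contain no data from which to derive it. The 300% needs only three markers in every patient.

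The label in the section 2.B parenthesis is a drafting fault. Correcting it changes no planned test, but it matters for clarity because the parenthesis holds the only clock rule. Neither part affects the sample size or the test of the primary endpoint. Whether 20 patients per arm can support a claim of comparable success is a separate question that this correction does not settle.

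**What to change.** In Protocol section 2.E, item ii, replace the markers-over-patients rate with the proportion of patients with three markers properly placed, over all randomised patients in whom placement was attempted, counted in their assigned arm. Compare that single yes/no outcome by Fisher's exact test and drop the separate test of successful deployment. Because the SAP declares intention-to-treat, also give the number of randomised patients in each arm with no attempt. If a marker-level rate is wanted, divide by markers attempted and report it descriptively, provided that attempted markers are recorded.

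In section 2.B, remove the technical-success label from the parenthesis and list the four ease and visualization items separately. Add needle visualization to the endpoint list there. Keep the placement-time start and stop rule as its own item, and say whether it defines the primary endpoint.

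The SAP should carry the same definition. As it is written in the past tense, any report should state which definition and denominator were used.

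The cost is a few sentences. No new data are needed for the per-patient outcome: the protocol already records the number of markers deployed and confirms their location by fluoroscopy and planning CT.
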